6.1 Inclusion Criteria

1) Signed Written Informed Consent

- a) The participant must sign the ICF prior to the performance of any study-related procedures that are not considered part of standard of care.
- b) The participant must sign the consent for tumor biopsy samples (see Section 9.8.2 for details).

2) Type of Participants and Target Disease Characteristics

- a) Participants must be at least 18 years old and have histologic or cytologic confirmation of a solid tumor that is advanced (metastatic, recurrent, and/or unresectable) with measurable disease per RECIST v1.1 (Appendix 5) or metastatic disease documented by either bone lesions on radionuclide bone scan and/or soft tissue lesions on CT/MRI per PCWG3 criteria for prostate cancer (Appendix 6) and have at least 1 soft-tissue tumor lesion accessible for biopsy. For Part 2B participants with HCC, intermediate disease is allowed.
- b) Eastern Cooperative Oncology Group Performance Status of 0 or 1 (Appendix 7)
- c) The BMS-986249 Monotherapy Dose Escalation (Part 1A):
 - i) All solid tumor histologies, except for participants with primary central nervous system (CNS) tumors or tumors with CNS metastases as the only site of active disease, will be permitted during the Dose Escalation Phase.
 - ii) Participants must have received, and then progressed, relapsed, or been intolerant to, at least 1 standard treatment regimen in the advanced or metastatic setting according to tumor type, if such a therapy exists.
 - 1) BC participants must have received or been intolerant to, all approved standard systemic treatments that have shown a documented benefit in OS per product label.

- iii) Participants in the monotherapy arm must be anti-CTLA-4-naive. Prior anti-PD-1 or anti-PD-L1 exposure is allowed in the monotherapy arm, but at time of first study treatment, participants must be at least 5 half-lives (approximately 100 days) from last dose of PD-1/PD-L1 therapy.
- d) The Combination Dose Escalation of BMS-986249 with Nivolumab (Part 1B):
 - i) Participants with biopsy-proven SCLC, CRC, CRPC, RCC, bladder cancer, gastric cancer (including gastro-esophageal junction), esophageal cancer, and melanoma will be permitted during dose escalation, except for participants with tumors with CNS metastases as the only site of active disease.

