 - Participants with NSCLC will also be permitted in this portion of the study but not as part of the initial DLT assessment; instead, NSCLC participants will be evaluated only as part of adding additional participants to a previously tested cohort.
 - ii) Participants with Gastric, Esophageal, or Urothelial cancer:
 - 1) Gastric and esophageal cancer participants must have received, and then progressed, relapsed, or been intolerant to, at least 1 standard treatment regimen in the advanced or metastatic setting, if such a therapy exists.
 - 2) Urothelial carcinoma participants must have received, and then progressed, relapsed, been intolerant to, or ineligible for, at least 1 platinum-containing chemotherapy regimen.
 - iii) Participants with NSCLC:
 - 1) NSCLC participants must have received, and then progressed, relapsed, or been intolerant to, at least 1 standard treatment regimen in the advanced or metastatic setting, if such a therapy exists.
 - 2) If the tumor is PD-L1 >50% by immunohistochemistry (IHC), they may be treatment-naive.
 - iv) All Part 1B participants must be naive to prior anti-CTLA-4 and anti-PD-1 or anti-PD-L1 therapies.
 - v) Participants with CRC:
 - 1) Participants must have received and then progressed on or after, or have been intolerant or refractory to, at least 1 standard systemic therapy for metastatic and/or unresectable disease (or have progressed within 6 months of adjuvant therapy), including oxaliplatin and irinotecan.
 - 2) Participants must have known MSI-H or dMMR status. KRAS, and BRAF status, if known, should be documented.
 - 3) Participants who have received prior anti-angiogenic therapy (eg, bevacizumab) and/or anti epidermal growth factor receptor therapy (eg, cetuximab or panitumumab) are eligible.
 - vi) Participants with SCLC:
 - 1) Histologically or cytologically documented SCLC, limited or extensive stage disease
 - 2) Received at least 1 prior platinum-containing chemotherapy regimen.

vii) Participants with CRPC:

- 1) Participants must have at least 1 soft tissue lesion, unrelated to bone, that qualifies as measurable disease per RECIST v1.1.
- 2) Participants must have received and progressed/been intolerant of (or not be a candidate for) at least 1 and not more than 3 standard therapies and have been considered for all other potentially efficacious therapies.
- 3) Previous treatment for hormone sensitive prostate cancer does not qualify without subsequent treatment for hormone refractory state.

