- 1) Participants must have a histologically confirmed adenocarcinoma of the prostate without small cell features and with current evidence of metastatic disease documented by either bone lesions on radionuclide bone scan and/or soft tissue lesions on computed tomography (CT)/magnetic resonance imaging (MRI). Metastases may be in regional lymph nodes (N1 per current AJCC staging criteria) and/or distant metastases (M1 per current AJCC staging criteria).
 - a) Participants whose disease spread is limited to regional pelvic lymph nodes (N1M0) must have a lymph node measuring at least 2 cm in short axis to be considered eligible.

2) Participants must have:

- a) Documented prostate cancer progression as per PCWG3 criteria within 6 months prior to screening, with at least 1 of the following:
 - i) PSA progression* defined by a minimum of 2 rising PSA levels with an interval of ≥ 1 week between each determination. The PSA value should be ≥ 2 ug/L (2 ng/mL).
 - *Participants who received an anti-androgen must have PSA progression after withdrawal (see below).
 - ii) Radiographic disease progression in soft tissue disease based on RECIST v1.1.
 - iii) Radiographic disease progression in bone defined as appearance of 2 or more new bone lesions on bone scan.
- b) Received and progressed on or after, or been intolerant to, a taxane-containing regimen and received no more than 2 prior chemotherapy regimens in the metastatic setting.
 - (i) If taxane-based chemotherapy was only given in the metastatic castrationsensitive setting, participants must also have progressed following prior treatment with a second generation hormonal therapy.
- 3) Prior second-generation hormonal manipulations (eg, abiraterone acetate, enzalutamide, apalutamide), ketoconazole, prostate cancer vaccine therapy, radiation therapy (including targeted radioligands), radium-223, anti-androgens (eg, flutamide), chemotherapy, and diethylstilbestrols or other estrogens are allowed up to 28 days prior to study treatment.

Note: Bicalutamide or nilutamide must be discontinued at least 6 weeks prior to treatment.

- a) Participants with a history of response to an anti-androgen or adrenal androgen production inhibitor and subsequent progression while on that anti-androgen should be assessed for anti-androgen withdrawal response for 4 weeks (6 weeks for bicalutamide or nilutamide), and must demonstrate progression off anti-androgen prior to enrollment.

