10.3.1 Analyses

The Part 2A efficacy analyses will be performed on the randomized population, with supplemental analyses on the treated population, while the efficacy analysis of Part 2B will be performed on the treated population (Table 10.3.1-1). The efficacy and safety analysis for Part 2B will be evaluated by tumor-specific cohort. Analysis of the treated participants from Part 1 will be presented separately. The following censoring rules will be applied for the definition of PFS and DoR:

- Subjects who did not progress or die will be censored on the date of their last evaluable tumor assessment.
- Subjects who did not have any evaluable on study tumor assessments and did not die will be censored on their date of randomization (for Part 2A) or first dosing (Part 1 and Part 2B).
- Subjects who receive subsequent anti-cancer therapy prior to documented progression or death will be censored at the date of the last evaluable tumor assessment conducted on or prior to the date of initiation of the subsequent anti-cancer therapy.

Additional details of the calculation of time-to-event endpoints such as DOR and PFS will be described in the Statistical Analysis Plan.

The efficacy and safety data from participants randomized in Part 2A Arms A, B, and E before Revised Protocol 07 will be analyzed using descriptive measures only.

Table 10.3.1-1: Efficacy - Statistical Analyses^a

Endpoint	Statistical Analysis Methods
Best observed response (BOR) BOR for a participant will be assessed per RECIST v1.1 or PCWG3 by investigator, unless otherwise specified	Summary and listing of BOR

Protocol Amendment No.: 09

Table 10.3.1-1: Efficacy - Statistical Analyses^a

Endpoint	Statistical Analysis Methods
ORR ORR is defined as the proportion of participants whose BOR is either CR or PR per RECIST v1.1 in the population of interest or PCWG3 for participants with prostate cancer.	Point estimate and CI by arm/cohort in Parts 2A and 2B Part 2A: Chi square test and sensitivity analysis using Cochran-Mantel-Haenszel test with the stratification factors as strata
DOR DOR for a participant with a BOR of CR or PR is defined as the time between the date of first response and the date of the first objectively documented tumor progression per RECIST v1.1 or PCWG3 or death, whichever occurs first.	Median and CI by K-M method for participants who responded, by arm/cohort

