2.3.2 Time Point Response

At each protocol specified time point, a response assessment occurs. Table 2.3.2-1 provides a summary of the overall response status calculation at each time point for patients who have measurable disease at baseline. When patients have non-measurable (therefore non-target) disease only, Table 2.3.2-2 is to be used.

Table 2.3.2-1:	Time Point Response:	Patients With Target (=	Ŀ Non-Target) Disease
Target Lesions	Non-Target Lesions	New Lesions	Overall Response
CR	CR	No	CR
CR	Non-CR/non-PD	No	PR
CR	Not evaluated	No	PR
PR	Non-PD or not all evaluated	No	PR
SD	Non-PD or not all evaluated	No	SD
Not all evaluated	Non-PD	No	NE
PD	Any	Yes or No	PD
Any	PD	Yes or No	PD
Any	Any	Yes	PD

CR = complete response, PR = partial response, SD = stable disease, PD = progressive disease and NE = inevaluable

Table 2.3.2-2: Time Point Re	sponse: Patients with I	Non-target Disease Only
Non-Target Lesions	New Lesions	Overall Response
CR	No	CR
Non-CR/non-PD	No	Non-CR/non-PD ^a
Not all evaluated	No	NE
Unequivocal PD	Yes or No	PD
Any	Yes	PD
CR = complete response, PD = progressive disease and NE = inevaluable		

Non-CR/non-PD is preferred over SD for non-target disease since SD is increasingly used as endpoint for assessment of efficacy in some trials so to assign this category when no lesions can be measured is not advised.

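### Part 2B CRPC response rate is computed on all treated participants, though some may be eligible without a target lesion and so cannot be scored as partial responders

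*Combined protocol and SAP*

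**What the plan says.** **Eligibility.** Section 6.1, criterion 2)a), asks for RECIST-measurable disease or, for prostate cancer, "metastatic disease documented by either bone lesions on radionuclide bone scan and/or soft tissue lesions on CT/MRI per PCWG3 criteria for prostate cancer". It adds that participants must "have at least 1 soft-tissue tumor lesion accessible for biopsy", with no size threshold. Criterion 2)f)ii) for Cohort 2 repeats the disease definition: "current evidence of metastatic disease documented by either bone lesions on radionuclide bone scan and/or soft tissue lesions". Its only size rule is for disease confined to regional pelvic nodes (N1M0), where participants "must have a lymph node measuring at least 2 cm in short axis to be considered eligible". In Part 1B the CRPC criterion was explicit: "Participants must have at least 1 soft tissue lesion, unrelated to bone, that qualifies as measurable disease per RECIST v1.1". Cohort 2 has no counterpart.

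**Analysis population.** Section 10.3.1 states that "the efficacy analysis of Part 2B will be performed on the treated population". Table 10.2-1 defines treated as having had at least one dose, and it lists no measurable-disease or response-evaluable set. Table 10.3.1-1 defines ORR as the proportion with a best response of CR or PR in the population of interest, using PCWG3 for prostate cancer.

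**Response rules.** In Appendix 6, PR is a decrease of at least 30% in the summed diameters of target lesions (Section 2.1). For participants without target lesions: "When patients have non-measurable (therefore non-target) disease only, Table 2.3.2-2 is to be used". That table offers CR, non-CR/non-PD, NE and PD.

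**The concern.** An ORR is easiest to read when everyone in the denominator can reach either form of response. Here a treated CRPC participant may have no target lesion, for example bone metastases with a biopsiable node of 10 to <15 mm short axis, which Appendix 6 classes as non-measurable. PR is closed to that participant, but the participant still counts in the denominator.

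The reported CRPC ORR then mixes two things: the activity of the regimen in measurable disease, and the proportion of participants who happened to have measurable disease. Two cohorts with the same activity could report different ORRs. The mix can differ from that of other CRPC series, and from that of the Part 1B CRPC participants, who had to have a measurable lesion.

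**Working it through.** **Step 1. Can a participant without a target lesion enter Cohort 2?** Yes. Bone metastases satisfy the disease criterion, and a small soft-tissue lesion can satisfy the biopsy criterion. The 2 cm node rule applies to N1M0 only.

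**Step 2. Which responses are open to that participant?** CR only. Section 2.1 of Appendix 6 ties PR to target lesions, and Table 2.3.2-2 has no PR row. CR remains possible: Section 2.2 requires non-target lesions to disappear and nodes to fall below 10 mm short axis.

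**Step 3. Is that participant in the denominator?** Yes, because the treated population is the only one named for Part 2B efficacy. By contrast, the Part 2A ORR estimand in Table 4-4 is limited to treated participants with an evaluable baseline tumor assessment. Table 4-5 gives Part 2B an estimand for the safety endpoint only.

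**Step 4. Size.** Let f be the share of treated CRPC participants without a target lesion, R the ORR in those with measurable disease, and C the CR rate in those without.

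Treated ORR = (1 − f) × R + f × C

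The documents give none of f, R or C. Assume R = 20%, f from 5% to 40%, and C of 0% or 5%:

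| f | C = 0% | C = 5% |
|---|---|---|
| 5% | 0.95 × 20 = 19% | 19 + 0.25 = 19.25% |
| 10% | 0.90 × 20 = 18% | 18 + 0.5 = 18.5% |
| 20% | 0.80 × 20 = 16% | 16 + 1 = 17% |
| 30% | 0.70 × 20 = 14% | 14 + 1.5 = 15.5% |
| 40% | 0.60 × 20 = 12% | 12 + 2 = 14% |

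The shift is R − treated ORR = f × (R − C). It is downward when C < R and zero when C = R.

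**Step 5. Price of restricting the denominator.** Table 10.3.1-1 uses a two-sided 60% CI. By the normal approximation (my choice; z = 0.8416), the half-width at an observed 20% is 0.8416 × √(0.16/n):

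- n = 40: 5.3 points
- n = 36 (f = 10%): 5.6 points
- n = 32 (f = 20%): 6.0 points
- n = 24 (f = 40%): 6.9 points

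**Plan's own figure.** No ORR power is legible to reproduce. Section 10.1.3 says only that power is reasonable at a one-sided 20% level, and the CRPC null and target rates are redacted.

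**The case against.** **The affected share may be small.** This stands. A biopsiable soft-tissue lesion is required and bone biopsies are not accepted (Table 2-1, Section 9.8.2), which should keep out purely bone-only disease. Core, incisional or excisional sampling also favours larger lesions. Accessible is still not the same as measurable, so the share need not be zero.

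**These participants can still respond.** This also stands. A small node that shrinks below 10 mm could count as CR, so the dilution is less than proportional to f.

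**The denominator may be deliberate.** An all-treated denominator is conservative and avoids selection after the fact. The ORR definition refers to a population of interest, and further SAP detail could name a subset. As written, though, the treated set is the only one named for Part 2B.

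**Stronger reading: the cohort loses power and is not comparable with its design rates.** A reader might infer this, but the documents do not support it. The redacted rates in Section 10.1.3 are stated for the CRPC and TNBC populations as the protocol defines them, which may already include non-measurable disease. The one visible CRPC benchmark (10% ORR, Section 5.4.9) has no stated denominator.

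An exact binomial illustration shows how much rests on this. Assume n = 40, one-sided 20%, null 10%, target 25% and no CRs in non-measurable disease. If both rates describe measurable disease only, power falls from 90% to 71%, 57% and 39% at f = 20%, 30% and 40%. If null and target are both scaled by 1 − f, power is 84%, 85% and 74%. That is close to the 85%, 87% and 75% obtained among measurable participants alone. These figures also move with the cut-off, because the attained alpha changes with n and the null rate. Moreover, Table 10.3.1-1 gives Part 2B ORR only a point estimate and CI, so no formal test is visible that the cohort could fail.

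**Conclusion.** The point holds as one about what the CRPC ORR measures. Eligibility admits participants for whom PR is unavailable, and the stated denominator includes them. Under the assumptions above, a 20% ORR in measurable disease reads 19% to 12% with no CRs in the affected group, and about 19% to 14% with 5% CRs. The direction requires only that CRs in non-measurable disease be rarer than responses in measurable disease. The size depends on f, which the documents do not give and which may be near the low end.

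No loss of power and no mismatch with the design benchmarks is established. CRPC ORR is a secondary endpoint; the primary safety endpoint and the PSA response rate are unaffected. This is a cheap improvement to a stated analysis rule.

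**What to change.** In Section 10.3.1 and Table 10.3.1-1:

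- Estimate CRPC ORR on treated participants with at least one measurable soft-tissue lesion at baseline.
- Report TTR and DOR for responders in that set.
- Give the all-treated ORR as supplementary, and report the number of treated CRPC participants without target lesions.
- Keep PSA response and PFS on all treated participants.

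The cost is analysis wording, a CRPC denominator below 40 if any participant lacks a target lesion, and the somewhat wider interval shown above. Eligibility and data collection do not change.

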6.2 Exclusion Criteria

1) Target Disease Exclusions

a) Participants with primary CNS malignancies, tumors with CNS metastases as the only site of disease, or active brain metastases will be excluded. Participants with controlled brain metastases, however, will be allowed to enroll. Controlled brain metastases are defined as no radiographic progression for at least 4 weeks following radiation and/or surgical treatment (or 4 weeks of observation if no intervention is clinically indicated) and no longer

taking steroids for at least 2 weeks prior to first dose of study treatment and with no new or progressive neurological signs and symptoms.

2) Prohibited Treatments

- a) Cytotoxic agents, unless at least 4 weeks have elapsed from last dose of prior anti-cancer therapy and initiation of study therapy.
- b) Noncytotoxic agents, unless at least 4 weeks or 5 half-lives (whichever is shorter) have elapsed from the last dose of prior anti-cancer therapy and the initiation of study therapy. If 5 half-lives is shorter than 4 weeks, agreement with the Sponsor/Medical Monitor (or designee) is mandatory. See Section 6.1 for additional requirements for prior treatments.
 - i) Not applicable per Revised Protocol 04: Continued ADT in men with CRPC after progression on an initial ADT regimen is allowed.
 - ii) Continued LHRH/GnRH agonist therapy in men with CRPC after progression on an initial ADT regimen is allowed.
 - iii) Goserelin (or other applicable GnRH agonist therapy) may be administered per institutional guidelines for prevention of premature menopause in premenopausal women.
- c) Prior immunotherapy treatments, unless at least 4 weeks or 5 half-lives (whichever is shorter) have elapsed from the last dose of immune therapy and initiation of study therapy. See Section 6.1 for additional requirements for prior immunotherapy treatments.
- d) Any botanical preparation (eg, herbal supplements or traditional Chinese medicines) intended to treat the disease under study within 2 weeks prior to treatment. If less than 2 weeks have elapsed from the last botanical supplement and the initiation of study treatment, the participant can be treated at the investigator's discretion and in agreement with the Sponsor/Medical Monitor (or designee).
 - i) Use of marijuana and its derivatives for treatment of symptoms related to cancer or cancer treatment are permitted if obtained by medical prescription or if its use (even without a medical prescription) has been legalized locally.
- e) Participants currently in other interventional trials, including those for coronavirus disease of 2019 (COVID-19), may not participate in BMS clinical trials until the protocol-specific washout period is achieved. If a study participant has received an investigational COVID-19 vaccine or other investigational product designed to treat or prevent COVID-19 prior to screening, enrollment must be delayed until the biologic impact of the vaccine or investigational product is stabilized, as determined by discussion between the investigator and the Medical Monitor (or designee).

3) Medical History and Concurrent Diseases

- a) Participants with concomitant second malignancies (except adequately treated nonmelanomatous skin cancers or in situ urothelial, breast, or cervical cancers) are excluded unless a complete remission was achieved at least 2 years prior to study entry, and no additional therapy is required or anticipated to be required during the study period.
 - i) In Part 2, the BMS-986249 Cohort Expansion Combination Therapy Phase, participants with concurrent malignancies that do not require treatment and are clinically stable and anticipated to be followed in an active surveillance manner for the next 12 months are eligible. Treatment should not be required at timing of consent and not be expected to be needed not only for the concurrent malignancy, but also for

complications caused by it. The investigator should inform the participant that the study treatment is not intended and not expected to be considered as treatment for the concurrent malignancy.

- b) Participants with other active malignancy requiring concurrent intervention.
- c) Prior organ allograft.
- d) Toxicity (except for alopecia) related to prior anti-cancer therapy and/or surgery, unless the toxicity is resolved, returned to baseline or Grade 1, or deemed irreversible.
 - i) Any active neuropathy > Grade 2 (National Cancer Institute [NCI] Common Terminology Criteria for Adverse Events [CTCAE] v4.03).
- e) Participants with the following:
 - i) Active, known, or suspected autoimmune disease.
 - 1) Participants with well-controlled asthma and/or mild allergic rhinitis (seasonal allergies) are eligible.
 - 2) Participants with the following disease conditions are also eligible:
 - (a) Vitiligo
 - (b) Type 1 diabetes mellitus
 - (c) Residual hypothyroidism due to autoimmune condition only requiring hormone replacement.
 - (d) Euthyroid participants with a history of Grave's disease (participants with suspected autoimmune thyroid disorders must be negative for thyroglobulin and thyroid peroxidase antibodies and thyroid stimulating Ig prior to the first dose of study treatment).
 - (e) Psoriasis not requiring systemic treatment or conditions not expected to recur in the absence of an external trigger are permitted to enroll.
 - ii) History of life-threatening toxicity related to prior immune therapy or any toxicity that resulted in permanent discontinuation from prior immune therapy (eg, anti-CTLA-4 or anti-PD-1/PD-L1 treatment or any other Ab or drug specifically targeting T cell co-stimulation or immune-checkpoint pathways) except those that are unlikely to re-occur with standard countermeasures (eg, hormone replacement after adrenal crisis).
 - iii) Conditions requiring systemic treatment with either corticosteroids > 10 mg daily prednisone equivalents or other immunosuppressive medications within 14 days of study treatment administration, except for adrenal replacement steroid doses of > 10 mg daily prednisone equivalent in the absence of active autoimmune disease.
 - 1) Treatment with a short course of steroids (< 5 days) up to 7 days prior to initiating study treatment is permitted.
 - iv) Uncontrolled or significant cardiovascular disease including, but not limited, to any of the following:
 - 1) Myocardial infarction or stroke/transient ischemic attack within the past 6 months.
 - 2) Uncontrolled angina within the past 3 months.
 - 3) Any history of clinically significant arrhythmias (such as ventricular tachycardia, ventricular fibrillation, or torsades de pointes).

- 4) History of other clinically significant heart disease (eg, cardiomyopathy, congestive heart failure with New York Heart Association functional classification III to IV [Appendix 8], pericarditis, or significant pericardial effusion).
- 5) History of myocarditis, regardless of etiology.
- 6) Cardiovascular disease-related requirement for daily supplemental oxygen therapy.
- 7) QT interval corrected for heart rate using Fridericia's formula (QTcF) prolongation > 480 msec, except for right bundle branch block.
- v) History of chronic hepatitis (except for HCC) as evidenced by the following:
 - 1) Positive test for hepatitis B surface antigen or any positive test result for HBV indicating presence of the virus.
 - 2) Positive test for qualitative hepatitis C viral load by polymerase chain reaction (PCR).
 - (a) Participants with positive hepatitis C Ab and negative quantitative hepatitis C by PCR are eligible. History of resolved hepatitis A virus infection is not an exclusion criterion.
 - (b) Additional testing or substitute testing per institutional guidelines to rule out infection is permitted.
- vi) Evidence of active infection that requires systemic antibacterial, antiviral, or antifungal therapy ≤ 7 days prior to the first dose of study treatment (except for viral infections that are presumed to be associated with the underlying tumor type required for study entry).
- vii) Not applicable per Revised Protocol 04: Known history of testing positive for human immunodeficiency virus (HIV) or known acquired immunodeficiency syndrome (AIDS).
 - Note: Testing for HIV must be performed at sites where mandated by local requirements.
- viii) Any major surgery within 4 weeks of the first dose of study treatment. Participants must have recovered from the effects of major surgery or significant traumatic injury at least 14 days before the first dose of study treatment.
- ix) Participants who have received live/attenuated vaccine within 30 days of first treatment.
 - 1) The use of inactivated seasonal influenza vaccines (eg, FluzoneTM) will be permitted on study without restriction
- x) Receipt of packed red blood cells or platelet transfusion within 2 weeks of the first dose of study treatment.
- xi) Any known or underlying medical, psychiatric condition and/or social reason that, in the opinion of the investigator or Sponsor, could make the administration of study treatment hazardous to the participants or could adversely affect the ability of the participant to comply with or tolerate the study.
- xii) Positive test for HIV with an AIDS-defining opportunistic infection within the last year, or a current CD4 count $< 350 \text{ cells/}\mu\text{L}$. Participants with HIV are eligible if:
 - 1) They have received antiretroviral therapy (ART) for at least 4 weeks prior to study treatment as clinically indicated.

- 2) They continue on ART as clinically indicated while enrolled on study.
- 3) CD4 counts and viral load are monitored per standard of care by a local healthcare provider while enrolled on study.

Note: Testing for HIV must be performed at sites where mandated by local requirements. HIV-positive participants must be excluded where locally mandated (see Appendix 14).

- xiii) Interstitial lung disease that is symptomatic or may interfere with the detection or management of suspected treatment-related pulmonary toxicity.
- xiv) Previous severe acute respiratory syndrome coronavirus 2 (SARS-CoV-2) infection either suspected or confirmed within 4 weeks prior to screening.
 - 1) Acute symptoms must have resolved and based on investigator assessment in consultation with the Medical Monitor, there are no sequelae that would place the participant at a higher risk of receiving investigational treatment.
- f) WOCBP who are pregnant or breastfeeding.

4) Allergies and Adverse Drug Reaction

- a) History of allergy to study treatment(s) or any of its components.
- b) History of severe hypersensitivity reaction to any mAb.

5) Other Exclusion Criteria

- a) Prisoners or participants who are involuntarily incarcerated. (Note: Under certain specific circumstances and only in countries where local regulations permit, a person who has been imprisoned may be included or permitted to continue as a participant. Strict conditions apply, and BMS approval is required).
- b) Participants who are compulsorily detained for treatment of either a psychiatric or a physical (eg, infectious disease) illness.

Eligibility criteria for this study have been carefully considered to ensure the safety of the study participants and that the results of the study can be used. It is imperative that participants fully meet all eligibility criteria.

